8.3.3. Pregnancy reports

Patients should be cautioned to report pregnancy immediately. If pregnancy is confirmed while taking the investigational product, the IP should be discontinued and the patient should be excluded from the trial. Within 24 hours of confirmation of pregnancy, the investigator must notify the CRO/Sponsor representative. This is done by completing the "Pregnancy Notification Form" and submitting it to the CRO/Sponsor representative.

Pregnancy is not considered to be an AE or SAE. However, pregnancy-related AEs must be treated as AEs or SAEs and reported to the Sponsor as appropriate.

Information should be collected on patients who become pregnant while participating in the trial. In addition, when children are born from these pregnancies, they should be evaluated for health status. The investigator should obtain the following information (if possible) from each pregnant woman who has taken the investigational product:

- results of an ultrasound scan performed early in pregnancy.
- information about the outcome of the pregnancy.

The following events will be considered SAEs:

- spontaneous abortion;
- ectopic pregnancy;
- congenital anomaly (defect);
- death of a child during the first month of life, regardless of the cause;
- death of a child over 1 month of age that the principal investigator believes is related to the effect of the investigational product.

Pregnancy forms should be sent to the CRO/Sponsor representative. Only pregnancies reported after initiation of the investigational products were observed.

The pregnancy should be followed up as part of a planned clinical trial until the outcome of the pregnancy is determined (up to 30 days after delivery), including spontaneous or induced abortion, and to obtain information on the delivery and the presence or absence of congenital malformations or anomalies or maternal and infant complications.

The procedure for submitting pregnancy forms is similar to the procedure for reporting SAEs.

9. STATISTICS

9.1. Calculation of sample size

The sample size calculation was based on the results of the Phase III clinical trial of Mexidol® [Multicentre randomized double-blind placebo-controlled parallel-group trial of the efficacy and safety of MEXIDOL® (solution for intravenous and intravenous administration / coated tablets) in long-term sequential therapy in patients with hemispheric ischaemic stroke in

the acute and early recovery periods - (EPICA)] dated 30.09.2016.

The trial plans to test the hypothesis of "superiority" of therapy with the investigational product vs. placebo therapy. The following indicator was chosen as the primary efficacy criterion: "The magnitude of change in the patient's **mRS** (Modified Rankin Scale) score at the end of therapy (Day 71) vs. baseline (in points)"

In the case of a superiority trial, the null hypothesis (H_0) and the alternative hypothesis (H_1) are formulated as follows:

$$H_0: \varepsilon = \mu_T - \mu_p \leq \delta, H_1: \varepsilon > \delta, \delta > 0, \text{ where}$$

- ε is the true difference between the value of the primary efficacy index (μ_T) in the group of patients taking the investigational product (T) and the value of the primary efficacy index (μ_p) in the group of patients taking placebo,
- δ - the boundary of "superiority" of therapy with the investigational product compared to placebo therapy by the primary efficacy indicator.

To prove superiority of therapy with an investigational product compared with placebo therapy, the lower bound of the 95% one-sided confidence interval (CI) for the difference in values of the primary efficacy criterion ($\mu_T - \mu_p$) must be greater than δ , where $\delta > 0$, i.e. CI must fall within the interval $(\delta, +\infty)$.

To calculate the sample size, data from the EPICA clinical trial were used for the ITT population (patients who received the investigational product or placebo at least once), as this population allows us to draw conclusions about the efficacy of the investigational therapy on the population closest to the patient population in real clinical practice. The results of the previously conducted EPICA clinical trial are summarized in Table 9.1.

Table 9.1. *Change in mRS score at the end of therapy relative to baseline [Visit 1 (Day 1) to Visit 5 (Day 67-71)] in patients enrolled in the ITT population.*

[μ - arithmetic mean; SD - standard deviation, DM - difference in mean averages]

Patient group	Group	$\mu \pm SD$	Efficacy evaluation:	
			95% CI for the difference in mean ($\mu_{\text{Mex.}} - \mu_p$)	Comparison between groups
ITT population (n = 144)	Group I (Mexidol®, n = 72)	2.278 ± 0.755	DM = 0.292 (0.027; 0.556)	p = 0.029 (Mann-Whitney U-test)
	Group II (Placebo, n = 72)	1.986 ± 0.847		

According to the results of the EPICA clinical trial, the mean value of the change in the mRS score at the end of the course of therapy relative to the baseline level in the group of therapy with the investigational product was (mean (SD)) 2.278 (0.755) points, in the placebo group - 1.986 (0.847) points 2.278 (0.755) points, in the group of placebo therapy - 1.986 (0.847) points, the difference (Mexidol® - placebo) is 0.292 points, 95% confidence interval for the difference (Mexidol® - placebo) is (0.027, 0.556). The "superiority" boundary (δ) was chosen as the lower boundary of the confidence interval constructed for the difference (Mexidol® - placebo). Thus, $\delta = 0.027$ points.

To test the hypothesis of "superiority" of therapy with the investigational product compared with placebo therapy **at a significance level of $\alpha = 0.05$ (5%) to ensure power $1-\beta = 0.8$ (80%)**, the sample size was calculated for the primary efficacy criterion given the parallel design, a 1:1 randomization scheme (i.e., $k = 1$ - the ratio of sample sizes of the groups n_T/n_p), the expected difference in efficacy between the compared products $\varepsilon = 0.292$ and with a mixed standard deviation (SD) of the in-group efficacy $\sigma = 0.802$ points.

The formula [Chow Sh.-Ch., Shao J., Wang H., 2008] was used in the calculation:

$$n_T = n_R \frac{\frac{(1 + 1/k) * (z_\alpha + z_\beta)^2 * \sigma^2}{(\varepsilon - \delta)^2}}{\frac{2 * (1.6449 + 0.8416)^2 * 0.802^2}{(0.292 - 0.027)^2}} \approx 114 \text{ people/gr,}$$

where z_α and z_β - quantiles of the normal distribution $N(0,1)$ (mean: 0, standard deviation: 1).

The minimum number of patients completing the trial in accordance with the protocol must be at least $N = 2 * 114 = 228$ patients (114 patients per group).

Given the possible attrition of patients in the trial, it is planned to **randomize 304 patients**, of whom **at least 228 should complete the trial according to the Protocol**.

Given the potential dropout of patients during the Screening phase, approval is planned for a clinical trial with a total of **336 screened patients**.

The trial plans to conduct an interim analysis of the data, based on which a decision will be made whether to end the trial (if the trial objective is met) or to enroll the additional number of patients needed to confirm the efficacy of the IP, followed by pooling of all data for the final analysis. The choice of this approach¹ is due to the change in the design of the planned clinical trial, duration of use and dosages of the investigational product compared to the previously conducted clinical trial (EPICA).

In the first phase, an interim analysis of the primary endpoint data will be performed on all randomized patients (304 patients) at the end of the trial:

- If the required power $\geq 80\%$ is achieved, a 95% one-sided confidence interval for the difference in values of the primary efficacy criterion ($\mu_T - \mu_P$) will be used to prove the hypothesis of 'superiority'; the results obtained will be analysed and used to write the final clinical trial report.
- If the calculated power is less than 80 per cent, the sample size will be recalculated based on the data obtained after the first stage to achieve a trial power of 80 per cent, using a correction for genus I error α ($\alpha = 0.0294$)². A protocol amendment will then be submitted to the Ministry of Health and, once approval is granted, the necessary additional number of patients will be enrolled, followed by pooling of all data for final analysis and writing of the final clinical trial report. A 97.06% one-sided confidence interval for the difference in values of the primary efficacy criterion ($\mu_T - \mu_P$) constructed from pooled patient data, i.e. obtained from the first and second stage results, using $\alpha = 0.0294$, will be used to prove the hypothesis of 'superiority'. The final clinical trial report will be written using data from all patients.

9.2. Statistical analysis software

Statistical processing of data obtained during the trial will be performed using the R statistical programming language (version 3.4.4 or higher), SAS statistical software (version 9.4 or higher), or other specific applicable software that ensures appropriate quality of the data obtained.

9.3. Review of deviations from the protocol and analysis plan

Statistical analyses will take into account violations / deviations from protocol, if any. If significant deviations from the protocol are detected that may affect the assessment of therapy efficacy, the patient should be excluded from the main statistical analysis of efficacy data (from the PP population).

¹ Potvin D et al. Sequential design approaches for bioequivalence studies with crossover designs. Pharmaceutical Statistics, 2007 (Method C).

² Pocock SJ. Group sequential methods in the design and analysis of clinical studies. Biometrika 1977;64:191199.

Statistical analysis methods may be changed if this would facilitate a more correct and informative analysis, any changes will be described and justified in the final clinical trial report.

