9.7. Statistical methods

The choice of statistical analysis method will be determined by the type of raw data and the type of distribution. The feasibility of using a range of statistical techniques will be assessed after data collection is completed, as the nature of the data distribution, sample homogeneity, etc. is not known in advance.

During the course of the analysis, it is possible to expand the list of methods used if this is necessary for the qualitative treatment of the data.

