9.8. Significance level and power of the criterion

The level of significance (genus I error α) was chosen to be 0.05 (5%) and the power of the criterion was chosen to be at least 0.8 (80%).

Since an interim data analysis is planned, a genus I error correction approach α ($\alpha = 0.0294$)¹ will be used to prove the hypothesis of "superiority" of investigational product therapy over placebo therapy on the primary efficacy criterion.

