Statistical evaluation of efficacy and safety parameters will be performed in accordance with the Drug Evaluation Guidelines (Volume I. - FGBU NCESMP, Moscow, 2014), Guidelines on the principles of application of biostatistics in clinical trials of medicinal products (Annex to the recommendation of the EEC Collegium from 03.11.2020 No. 2014) and general recommendations on biomedical statistics (ICH Topic E9 Statistical Principles for Clinical Trials, CPMP/ICH/363/96, 1998; Sergienko V.I., Bondareva I.B. Mathematical Statistics in Clinical Trials, Moscow: GEOSTAR-Media, 2006).

3. Deviations from protocol

A statistical plan has been prepared and will be agreed prior to the statistical analysis. Statistical analyses were planned according to the Clinical Trial Protocol. Deviations from the protocol in statistical analyses are not planned. Any deviation from the protocol is permitted only in an emergency or after written authorization from the Sponsor. If there is a deviation from the planned statistical analysis, all changes will be identified compared to the methods described in the statistical analysis plan. Similarly, if any additional changes are required after the analysis has been performed, this will be reflected in the Clinical Trial Report. All deviations of the present from the statistical analysis plan with their justification will be reported in the Clinical Trial Report. No changes will be made to the list of parameters to be evaluated. Statistical analysis methods may be changed if this would facilitate a more correct and informative analysis, any changes will be described and justified in the final Clinical Trial Report.

Version 1.0 of 12.11.2021

[figure not shown]
Protocol-Specific Version for Protocol #PHS-APIS-004-MEX-SOL-TAV. version 1.3 dated 07.06.2021

CONFIDENTIAL

page 12 of 58

Plan for statistical analysis of efficacy and safety parameters

4. Trial procedures

5. Randomization

Table 1. Randomization scheme developed by Smooth Drug Development

Country	Block number	Randomization code	Therapy
Republic of Kazakhstan	001	616	B
Republic of Kazakhstan	001	174	A
Republic of Kazakhstan	001	637	B
Republic of Kazakhstan	001	869	A
Republic of Kazakhstan	2	455	A
Republic of Kazakhstan	2	548	B
Republic of Kazakhstan	2	687	A
Republic of Kazakhstan	2	809	B
Republic of Kazakhstan	3	810	B
Republic of Kazakhstan	3	680	A
Republic of Kazakhstan	3	294	A
Republic of Kazakhstan	3	513	B
Republic of Kazakhstan	4	180	A
Republic of Kazakhstan	4	467	B

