Secondary efficacy and safety endpoints and their changes will be presented using descriptive statistics by visit and therapy group. On trial visits, qualitative (dichotomous) measures will be compared between groups on the basis of Pearson's χ^2 test, if the frequency

Plan for statistical analysis of efficacy and safety parameters

of a feature in at least one subgroup is 5 or less, Fisher's exact test (or Fisher-Freeman-Galton test for tables of arbitrary dimensionality). Differences with p values of <0.05 will be considered statistically significant.

To compare quantitative data distributed according to the normal distribution law, it is planned to use standard parametric criteria: Student's t-test for dependent/independent samples, analysis of variance (ANOVA) for repeated measures.

It is planned to use standard nonparametric criteria to compare quantitative data distributed according to a law other than normal: Mann-Whitney U-test, Wilcoxon T-test, Friedman's test.

Benjamini-Yekuteli correction will be used for multiple statistical hypothesis testing.

A one-sided test will be applied to analyse the primary endpoint and two-sided statistical tests will be applied to analyse all secondary endpoints.

Scatter plots (boxplots) will be presented for all quantitative measures of efficacy and safety. Data whose distribution differs from normal at least at one visit in one of the groups will be presented as median and interquartile range; data whose distribution is normal at all visits will be presented as mean \pm standard deviation.

Pharmacodynamic effects will be analysed in a subpopulation of patients participating in the evaluation of the pharmacodynamic effects of the investigational therapy.

The resulting data will be analysed using the methods outlined for the application of the efficacy data assessment.

The p-level values <0.05 will be considered statistically significant.

The trial did not include interim statistical analyses.

The application of methods of statistical analysis of the obtained data will be determined by their nature, type and features of their distribution. The feasibility of using a number of statistical methods will be assessed after the completion of the data set, due to the unknown nature of their distribution, sample homogeneity, etc. During the course of the analysis, it is possible to expand the list of methods used if it is necessary for qualitative data processing.

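### The primary analysis has a stated default rule, but Protocol 9.3 and SAP 3 let methods change after results are known, which lifts its type I error by an amount that depends on the alternatives tried

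*Protocol*

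**What the plan says.** **The default rule.** Protocol 9.1 and 9.7.2 and SAP 7 require the lower bound of a one-sided 95% confidence interval for the difference in mean mRS change to exceed delta, with delta = 0.027 points. The level is 97.06% if a second stage is run. The per-protocol population is primary (Protocol 9.7.2, SAP 9 and 11). SAP 9 adds: "A one-sided test will be applied to analyse the primary endpoint and two-sided statistical tests will be applied to analyse all secondary endpoints".

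**The permissions.** Protocol 9.3 says "Statistical analysis methods may be changed if this would facilitate a more correct and informative analysis", with changes described and justified in the final report; SAP 3 repeats this. SAP 3 also provides that "if any additional changes are required after the analysis has been performed, this will be reflected in the Clinical Trial Report". Protocol 9.7 says "The feasibility of using a range of statistical techniques will be assessed after data collection is completed", and SAP 9 says "it is possible to expand the list of methods used if it is necessary for qualitative data processing".

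**The limits.** SAP 3 says deviations in the statistical analysis are not planned and that "Any deviation from the protocol is permitted only in an emergency or after written authorization from the Sponsor". It requires changes to be identified against the planned methods and justified, and it fixes the list of parameters to be evaluated. Protocol 11.7 requires a written amendment, approved before it takes effect, for any change to the protocol.

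**The concern.** A single confirmatory test keeps its stated error rate only if the analysis is settled before anyone can see which choice favours the product. None of the change clauses mentions database lock, release of treatment codes or the primary criterion. A sponsor-authorised switch made after the named analysis has missed, then described and justified in the report, can therefore be presented as following the plan. Its superiority claim would not carry the stated 5%.

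Two features add to this. The design has a stage 1 look at the primary endpoint, and SAP Table 4 sets the difference in means and its interval beside the stage 1 power, so the observed effect can be known while the stage 2 method is still open. The rule is also not closed at its core: no section says how the interval is computed, and footnote 4 to SAP Table 4 gives a different criterion (the upper bound of a two-sided 95% interval).

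**Working it through.** **1. The plan's own figure.** Inputs from Protocol 9.1: one-sided alpha 0.05 (z = 1.6449), power 80% (z = 0.8416), epsilon = 0.292, delta = 0.027, SD = 0.802, allocation 1:1.

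n per arm = 2 × (1.6449 + 0.8416)² × 0.802² / (0.292 − 0.027)² = 113.26, rounded up to 114. This reproduces the stated figure, so the 5% is a one-sided rate.

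**2. What the 5% means under the default rule.** It is the rejection rate when the true difference equals delta. The standard error is 0.802 × √(2/114) = 0.106, so delta is 0.027 / 0.106 = 0.25 standard errors. At a true difference of zero, one fixed test rejects with probability 1 − Φ(1.6449 + 0.25), about 2.9%.

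**3. Effect of choosing the best of several tests.** If superiority is claimed whenever any of k tests rejects, the rate is P(max Z_j > 1.6449). With equally correlated tests (multivariate normal):

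| Correlation | Best of 2 | Best of 3 | Best of 4 |
|---|---|---|---|
| 0.99 | 5.6% | 5.9% | 6.1% |
| 0.95 | 6.3% | 7.1% | 7.6% |
| 0.90 | 6.8% | 8.0% | 8.8% |

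The rate cannot fall below that of the single test, and it depends on how many alternatives are tried and how alike they are.

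**4. Patient-level simulation.** Null trials, 114 per arm, integer mRS, SD of change close to 0.8. Baseline mRS of 3, 4 and 5 in roughly 35%, 50% and 15% of patients is an assumption. Each test is one-sided 5% against no difference. The ranges cover several runs and several assumed relations between baseline and change.

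| Candidates | Rate for best result |
|---|---|
| t-test or Mann-Whitney on change (both named in the SAP; correlation about 0.99) | 5.3-6.2% |
| plus baseline-adjusted ANCOVA (named in neither document) | about 6-8% (5.5% with no baseline-change correlation, 8.4% at 0.67) |
| plus rank test of final mRS (a different parameter) | 8.2-9.6% |

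**5. Same exercise with the margin kept.** At zero true difference and delta = 0.027, a single fixed test rejects about 3% of the time, and the better of t-test and ANCOVA 3.2-4.2%. Mann-Whitney is left out because its p-value gives no bound on a mean difference.

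**The case against.** **The deciding test is fixed.** A reader might infer from the change clauses that it is not. The documents do not support that: endpoint, population, margin, sidedness and confidence bound are each stated. The defect is that the default can be overridden and that the construction of the bound is left open.

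**The inflation is small.** A reader might put the error rate at 8-9%. That figure needs a switch to final mRS, whereas the primary criterion is change from baseline and SAP 3 says the list of parameters will not change. It belongs to a change of endpoint. The figures in step 4 also test against no difference; with delta kept, rejection at zero true difference stays under 5%. Both points stand and limit the size. They do not remove the problem: the planned 5% applies at a difference equal to delta, and selection raises the rate above it there.

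**There are safeguards.** Changes must be justified and authorised, and Protocol 11.7 may require an approved amendment before the rule in 9.7.2 is replaced. That is a fair reading, but 9.3 itself permits a change of method and asks only for description and justification in the report. The two sections are never reconciled, and the authorising party is the sponsor with no time limit set.

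**SAP 3 contradicts itself.** It does not. Saying that deviations are not planned and then giving a procedure in case one occurs is consistent. The sentence on changes after the analysis is worded as a reporting duty and does not say a later method replaces the planned one; equally, it does not say that it may not.

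**Conclusion.** The concern holds in limited form. A default primary rule exists, but the documents permit methods to be changed or added after data collection and foresee changes after the analysis, with no exemption for the primary criterion and no unblinding cut-off. Picking the most favourable method after seeing results raises the type I error above nominal: to about 5.3-6.2% for the two tests the SAP names, and about 6-8% with a baseline-adjusted analysis added.

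These figures rest on tests against no difference, 114 per arm and an assumed baseline mRS mix. They describe what selection could do; the documents do not say it will happen. The direction is certain and the size is modest. It should be corrected because a favourable switch after the result could comply with the text as written and still not be defensible as confirmatory.

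**What to change.** In Protocol 9.3 and 9.7 and SAP 3 and 9:

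- State that the primary criterion is decided only by the pre-specified lower one-sided confidence bound for the difference in mRS change, and name how that bound is computed.
- Correct footnote 4 of SAP Table 4 to match.
- Allow a change of method only through a dated SAP version approved before database lock and release of treatment codes, and before the stage 1 look for any stage 2 analysis. Where the protocol's own rule changes, require an amendment under 11.7 as well, and cross-refer 9.3 to 11.7.
- Label any later method post hoc and report it beside the pre-specified result. It may neither replace that result nor support a superiority claim.
- Limit changes after the analysis to correcting programming errors.

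This costs a few sentences and no patients or procedures. Exploratory work remains possible. The one loss is the sponsor's freedom to change the deciding analysis after unblinding.
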